12.5 Analysis of Exploratory Objectives

Pharmacodynamic and correlative biological studies

Analysis of the pharmacodynamic and correlative biological studies will be descriptive.

Responsible investigator: [name], PhD
Responsible statistician: [name]

12.6 Anticipated Completion Dates

Anticipated primary completion date: December, 2018
Anticipated study completion date: January, 2020

13.0 OBTAINING INFORMED CONSENT

13.1 Consent Prior to Research Interventions

Initially, informed consent will be sought for the institutional banking protocol (TBANK research study), PGEN5, and for other procedures as necessary for standard medical care. During the screening process for eligibility, informed consent for SCREEN protocol OR for SELHEM is required before any research tests are performed.

13.2 Consent at Enrollment

The process of informed consent for SELHEM will follow institutional policy. The informed consent process is an ongoing one that begins at the time of diagnosis and ends after the completion of therapy. Informed consent should be obtained by the attending physician or his/her designee, in the presence of at least one non-physician witness. Initially, informed consent will be sought for the institutional banking protocol (research study), blood transfusion and other procedures as necessary. After the diagnosis of relapsed or refractory leukemia is established, we will invite the patient to participate in the SELHEM protocol.

Throughout the entire treatment period, participants and their parents receive constant education from health professionals at SJCRH and collaborating sites, and are encouraged to ask questions regarding alternatives and therapy. All families have ready access to chaplains, psychologists, social workers, and the St. Jude ombudsperson for support, in addition to that provided by the primary physician and other clinicians involved in their care. We will also obtain verbal assent from children 7 to 14 years old and written assent for all participants ≥ 14 years of age.

13.3 Consent at Age of Majority

Participants who reach the age of majority while on study will be re-consented for continued participation on SELHEM at the time of their next clinic visit after turning 18 year according to Cancer Center and institutional policy.

13.4 Consent When English is Not the Primary Language

When English is not the participant, parent, or legally authorized representative's primary language, the Social Work department will determine the need for an interpreter. This information will be documented in the participant's medical record. Either a certified interpreter or the telephone interpreter's service will be used to translate the consent information. The process for obtaining an interpreter and for the appropriate use of an interpreter is outlined on the Interpreter Services, OHSP, and CPDMO websites.

APPENDIX I: SELINEXOR Dosing Guidelines

Phase II Cohort: Dose Level 2 (40 mg/m²)

BSA range	Total mg dose
0.45 – 0.55	20
0.56 – 0.68	25
0.69 – 0.81	30
0.82 – 0.93	35
0.94 – 1.06	40
1.07 – 1.18	45
1.19 – 1.31	50
1.32 – 1.43	55
1.44 – 1.56	60
1.57 – 1.68	65
1.69 – 1.81	70
1.82 – 1.93	75
1.94 – 2.06	80
2.07 – 2.18	85
2.19 – 2.31	90
2.32 – 2.43	95
2.44 and greater	100

APPENDIX II: PERFORMANCE STATUS CRITERIA

PERFORMANCE STATUS CRITERIA					
Karnofsky and Lansky performance scores are intended to be multiples of 10					
ECOG (Zubrod)		Karnofsky		Lansky	
Score	Description	Score	Description	Score	Description
0	Fully active, able to carry on all pre-disease performance without restriction	100	Normal, no complaints, no evidence of disease	100	Fully active, normal
		90	Able to carry on normal activity, minor signs or symptoms of disease	90	Minor restrictions in physically strenuous activity
1	Restricted in physically strenuous activity by ambulatory and able to carry out work of a light or sedentary nature, e.g., light housework, office work	80	Normal activity with effort; some signs or symptoms of disease	80	Active, but tires more quickly
		70	Cares for self; unable to carry on normal activity or do active work	70	Both greater restriction of and less time spent in play activity
2	Ambulatory and capable of self-care but unable to carry out any work activities; up and about more than 50% of waking hours	60	Requires occasional assistance, but is able to care for most of his/her needs	60	Up and around, but minimal active play; keeps busy with quieter activities
		50	Requires considerable assistance and frequent medical care	50	Gets dressed, but lies around much of the day; no active play, able to participate in all quiet play and activities
3	Capable of only limited self-care, confined to bed or chair more than 50% of waking hours	40	Disabled, requires special care and assistance	40	Mostly in bed; participates in quiet activities
		30	Severely disabled, hospitalization indicated; death not imminent	30	In bed; needs assistance even for quiet play
4	Completely disabled; cannot carry on any self-care; totally confined to bed or chair	20	Very sick, hospitalization indicated. Death not imminent	20	Often sleeping; play entirely limited to very passive activities
		10	Moribund, fatal processes progressing rapidly	10	No play; does not get out of bed

APPENDIX III: TESTS PERFORMED FOR ROUTINE CARE AND FOR RESEARCH

Routine care

History & physical (including vital signs, BSA, PS)
CBC, differential, platelets
Serum chemistries
Amylase/lipase
Creatinine kinase, urate
TSH
Coagulation studies
GFR or creatinine clearance
Ophthalmologic exam
Pregnancy testing
EKG
Chest x-ray
Pulse oximetry
Lumbar puncture for IT chemotherapy, CSF cell count and differential
Bone marrow procedure for morphology, response assessment, MRD
Peripheral blood for MRD, if done
Commercially available agents – fludarabine, cytarabine, ITHMA

Research

Investigational agent – Selinexor
Pharmacokinetic studies (phase I only)
Pharmacodynamic studies (phase I only)
Correlative biological samples (phase II only)

APPENDIX IV: SELINEXOR DOSE MODIFICATION GUIDELINES FOR ADVERSE EVENTS ASSOCIATED WITH SELINEXOR

Toxicity and Intensity	Dose Modification
Fatigue (common)	
Grade 1	Insure adequate caloric intake and assess volume status. Adjust other medications. Consider addition of low dose corticosteroids (dexamethasone 5-10 mg/m ² /day with each dose of selinexor). Rule out other causes of fatigue such as adrenal insufficiency.
Grade 2	Insure adequate caloric and fluid intake and assess volume status. Add corticosteroids on day of selinexor (e.g., dexamethasone 5-10 mg/m ² /day). If fatigue dose not resolve to Grade 1, give dexamethasone on the day of and the day after selinexor dosing. If this does not improve fatigue, add a stimulant or bupropion q am, or reduce the dose of selinexor by one level (Table A2.1).
Grade 3	Insure adequate caloric and fluid intake and assess volume status. Initiate glucocorticoids as described for Grade 2. Interrupt selinexor dosing until resolved to Grade ≤ 2, reduce dose of selinexor by 1 level (Table A2.1), and add corticosteroids on day of and day after selinexor dosing.
Anorexia (common)	
Grade 1	Assess dietary options (e.g., try a variety of other foods). Add high-calorie supplements (e.g., Ensure [®]). If fatigue or nausea also present, consider low doses of corticosteroids (as for fatigue) on day of ± day after selinexor dosing.
Grade 2	Add high-calorie supplements (e.g., Ensure [®]). Consider olanzapine 1.25 to 5 mg po qhs or mirtazapine 7.5-15mg po qhs (especially if nausea or sleep disturbance present). Consider megestrol acetate, 10 to 15 mg/kg/day; 800 mg/day maximum dose. Consider low dose corticosteroids (see fatigue), anabolic steroids such as oxandrolone, or dronabinol (Marinol [®]) or other cannabinoid. Selinexor may be skipped intermittently while supportive medications are instituted, usually for <1 week. If Grade 2 anorexia does not resolve after institution of supportive medications, reduce selinexor dose by 1 level (Table A2.1).
Grade 3	Interrupt dosing with selinexor. Add high calorie supplements. Use supportive medications alone or in combinations. Restart selinexor at 1 dose level reduction (Table A2.1) once anorexia resolves to Grade ≤ 2. If Grade 2 anorexia persists with supportive medications, reduce dose of selinexor another level (Table A2.1).
Nausea - acute (common)	
Grade 1	5-HT ₃ antagonists, D ₂ antagonists, olanzapine 1.25 to 5mg daily, corticosteroids (e.g., dexamethasone 5-10 mg/m ² /day with each dose of selinexor ± the day after dosing), NK ₁ antagonists, or dronabinol (Marinol) or combinations can prevent nausea in the majority of patients.
Grade 2	Implement one or more combinations of anti-nausea medications. If nausea does not resolve to Grade ≤ 1, reduce dose of selinexor by one dose level (Table A2.1).
Grade 3	Implement one or more combinations of anti-nausea medications and interrupt dosing of selinexor. selinexor may be restarted with one dose level reduction (Table A2.1) when nausea is Grade ≤ 2 and adequate caloric and fluid intake have been achieved.

Hyponatremia (common)	
Grade 1 (Lower Limit of Normal to 130 nM)	Be certain sodium level is corrected for hyperglycemia (serum glucose >150mmol/L). Rule out other causes of low sodium (e.g., cardiac, hepatic, adrenal, renal and thyroid diseases, SIADH), Fanconi Syndrome, hyperglycemia, diuretic use). Maintain selinexor dose level, assure adequate fluid, electrolyte and caloric intake, adjust other medications, consider salt supplementation one – two times per day.
Hyponatremia 126-129nM without Symptoms (Grade 3)	Be certain sodium level is corrected for hyperglycemia. Rule out other causes of low sodium (e.g., cardiac, hepatic, adrenal, renal and thyroid diseases, SIADH), Fanconi Syndrome, hyperglycemia, diuretic use). Hold selinexor until Grade ≤ 1 (≥ 130 nM) and initiate aggressive salt supplementation two-three times per day.
Grade 3 (120-125 nM) or any Grade 3 with Symptoms	Be certain sodium level is corrected for hyperglycemia. Rule out other causes of low sodium (e.g., cardiac, hepatic, adrenal, renal and thyroid diseases, SIADH), Fanconi Syndrome, hyperglycemia, diuretic use). Hold selinexor until resolved to Grade ≤ 1 (≥ 130 nM) then reduce selinexor dose by 1 level. Initiate aggressive salt supplementation two-three times per day. If serum sodium stabilizes for at least 4 weeks, then original dose of selinexor may be resumed.
Diarrhea (common)	
Grade 1 (despite maximal anti-diarrheal medication)	At the first sign of abdominal cramping, loose stools, or onset of diarrhea, it is recommended that the patient be treated according to institutional standard of care, e.g., loperamide (Immodium®). Maintain dose level of selinexor.
Grade 2 (despite maximal anti-diarrheal medication)	Reduce to selinexor to one weekly until resolved to \leq Grade 1, then re-start twice weekly at the current dose level. If diarrhea returns as \geq Grade 2, then reduce selinexor dose by one dose level and dose once weekly until resolved to \leq Grade 1, then re-start twice weekly at reduced dose level
Grade 3/4 (despite maximal anti-diarrheal medication)	Delay selinexor until resolved to \leq Grade 2, then follow guidelines above.
Thrombocytopenia	
Grade 3 Thrombocytopenia Without bleeding	Implement platelet growth factors or transfusions. Begin (or maintain) once weekly dosing at the same dose level until resolved to Grade ≤ 2 .
Grade 4 Thrombocytopenia Without bleeding	Implement platelet growth factors or transfusions. Hold dosing until Grade ≤ 3 and follow above guidelines if Grade 3.
\geq Grade 3 Thrombocytopenia associated with petechiae or purpura	Implement platelet growth factors and/or transfusions. Hold selinexor for 5 days after last bleeding. Restart dosing one dose level below.
Neutropenia	
Grade 3 neutropenia without fever	Implement growth factors.
Grade 4 neutropenia without fever	Implement growth factors. If appropriate, initiate prophylactic anti- microbial agents.
Grade ≥ 3 febrile neutropenia	Implement growth factors. Initiate appropriate broad spectrum anti- microbial agents. Hold selinexor until fever resolves and patient is clinically stable. Restart dosing one dose level below.

Other selinexor-related adverse events	
Grade 1 or 2	Maintain dose level and initiate standard supportive care.
Grade 3	Delay dose until resolved to \leq Grade 1, then reduce by 1 dose level (Table A2.1).
Grade 4	Discontinue selinexor and rule out other causes. If other causes of Grade 4 adverse event are uncovered, selinexor may be re-initiated at 1 dose level reduction (Table A2.1).

All dose modifications should be based on the worst preceding toxicity. Isolated values of \geq Grade 3 alkaline phosphatase values will NOT require dose interruption. Determination of liver vs. bone etiology should be made, and evaluation of gamma-glutamyl transferase (GGT), 5'-nucleotidase (5'NT), or other liver enzymes should be performed. Patients are allowed dose reductions to a minimum dose of 15 mg/m² as described in Table A2.1. a. Common Terminology Criteria for Adverse Events (CTCAE Version 4.03) otherwise specified values.
	

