[REDACTED]
PI: [name], PhD
[REDACTED]

SELHEM: A PHASE I/II STUDY OF THE SELECTIVE INHIBITOR OF NUCLEAR EXPORT SELINEXOR (KPT-330) IN COMBINATION WITH FLUDARABINE AND CYTARABINE IN PEDIATRIC PATIENTS WITH REFRACTORY LEUKEMIA OR MYELODYSPLASTIC SYNDROME

Principal Investigator: [name], PhD

Institution/Sponsor-IND holder: St. Jude Children's Research Hospital. IND# 122,979

Brief overview: Phase I/II study to characterize the toxicity profile and to determine the maximum tolerated dose (MTD) and recommended phase II dose (RP2D) of selinexor when given with fludarabine and cytarabine in pediatric patients with relapsed or refractory hematologic malignancies including acute myeloid leukemia (AML), acute lymphoblastic leukemia (ALL), mixed phenotype acute leukemia (MPAL) and myelodysplastic syndrome (MDS).

Intervention: Interventional, primary therapeutic.

Drug: Selinexor

Drug: Fludarabine

Drug: Cytarabine

Procedure: LP with administration of ITHMA or cytarabine

Brief outline of treatment plan:

Selinexor will be given orally on days 1, 3, 8, 10, 22, and 24. The starting dose of Selinexor is 30 mg/m²/dose po given twice weekly and escalated or de-escalated based on tolerability.

Dose level	Selinexor (mg/m ² /dose on days 1, 3, 8, 10, 22, 24)	Fludarabine (mg/m ² /dose on days 16-20)	Cytarabine (g/m ² /dose on days 16-20)
-1	20	30	2
1	30	30	2
2	40	30	2
3	55	30	2
4	70	30	2

Fludarabine (30 mg/m²/dose IV over 30 minutes daily for 5 days) and **cytarabine** (2 gram/m²/dose IV over 4 hours daily for 5 days) will be given on days 16 through 20. Fludarabine and cytarabine may be given before day 15 if the treating physician, after consulting with the principal investigator (PI), believes it is in the patient's best interest based on disease progression.

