4.0 TREATMENT PLAN

4.1 Overview

Patients must have fully recovered from the acute effects of all prior therapy before starting selinexor. In addition, at least 14 days must have elapsed since the completion of myelosuppressive therapy or gemtuzumab ozogamicin and the first dose of selinexor. At least 24 hours must have elapsed since the completion of low-dose or non-myelosuppressive therapy, such as hydroxyurea, vincristine, steroids, or low-dose cytarabine (up to 100 mg/m²/day), and the first dose of selinexor. For patients who have received prior HSCT, there can be no evidence of GVHD and greater than 60 days must have elapsed since the HSCT.

This study will include two phases. The dose-escalation phase will characterize the dose-limiting toxicities (DLTs) and determine the maximum tolerated dose (MTD) and recommended phase 2 dose (RP2D) of selinexor when given in combination with fludarabine and cytarabine. The RP2D will be chosen based on the MTD and totality of the data (clinical, PK, and PD data from this and other trials). The phase II cohort will further assess the safety and will explore the efficacy of this combination.

Selinexor will be given orally on days 1, 3, 8, 10, 22 and 24 of each cycle.

Fludarabine (30 mg/m²/dose IV over 30 minutes daily) and **cytarabine** (2 gram/m²/dose IV over 4 hours daily) will be given on days 16 (\pm 2 days) through 20 (\pm 2 days). Chemotherapy may be delayed if clinically indicated.

For patients who achieve CR or CRi with negative MRD or with MRD that has decreased at Day 15, the treating physician may continue single agent selinexor without fludarabine and cytarabine. In this case, selinexor should be given on days 1, 3, 8, 10, 15, 17, 22 and 24.

Patients who achieve CR or CRi status (as defined in Section 8.1) at day 15 (regardless of MRD status) may proceed directly to HSCT at the discretion of the treating physician.

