4.4 Phase II Cohort

The Phase II portion of the study will enroll patients at a **selinexor dose of 40 mg/m²/dose** on the same administration schedule as the dose escalation cohort.

Evaluation of response to single agent selinexor: unless there is evidence of progressive disease by examination of the blood, participants should undergo bone marrow evaluation on day 15 (\pm 2 days). This evaluation must be performed prior to administration of fludarabine and cytarabine.

Evaluation of response to Cycle 1: participants should undergo response evaluation between days 42 and 56 of Cycle 1 (with the exception of any patient who obtains complete response at Day15 and elects to continue single agent selinexor and forego fludarabine and cytarabine therapy). Patients may be evaluated earlier if there is evidence of hematopoietic recovery or at discretion of treating physician. In cases with hypocellular marrows (<10% cellularity), repeat bone marrow examinations should be considered when there is evidence of hematopoietic recovery.

Table 4. Treatment administration

Drug	Dose	Route	Schedule
Selinexor	40 mg/m ²	PO	Days 1, 3, 8, 10, 22 and 24
Fludarabine	30 mg/m ² /dose	IV over 30 minutes	Days 16-20 ^a
Cytarabine	2 gram/m ² /dose	IV over 4 hours ^b	Days 16-20 ^a

^a *May be given earlier or later, as clinically indicated*

^b *Cytarabine should start at least 3.5 hours after completion of fludarabine*

Selinexor should be administered with food or within 30 minutes after a meal. The dose will be determined according to Appendix I and rounded to the nearest 10 mg.

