4.6.2.3 Dose modifications (See Appendix IV)

During Cycle 1 patients should receive 5 of the 6 intended doses of selinexor; failure to receive 5 doses by Day 35 because of toxicity will be considered a DLT (*phase I only*).

Note that at least 48 hours must pass between doses. Doses should be delayed, rather than omitted, for the following non-hematologic toxicities. Patients should also be treated aggressively with supportive care to reduce toxicities.

Weight loss: if a participant develops Grade 3 weight loss, the next dose of selinexor should be delayed until the weight loss resolves to Grade ≤ 2 . If weight loss does not improve to Grade ≤ 2 within 7 days, this participant will have experienced a DLT (*phase I only*).

Electrolyte abnormalities: if a participant develops Grade ≥ 3 uncorrectable electrolyte abnormalities, the next dose of selinexor should be delayed until the abnormalities resolve to Grade ≤ 2 . If abnormalities do not improve to Grade ≤ 2 within 7 days despite attempts to correct, this participant will have experienced a DLT (*phase I only*).

Infection: the occurrence of Grade 4 infection will not be considered a DLT (*phase I only*). Selinexor should be delayed in any participant with Grade 4 infection or clinical sepsis until condition has clinically stabilized. If during Cycle 1, selinexor is suspended

due to Grade 4 infection or clinical sepsis and participant misses ≥ 3 doses of study drug, the participant will be deemed not evaluable and removed from study. These patients will be replaced during the DLT period, but will be included in the evaluation of the safety profile of the regimen and determining the recommended phase 2 dose (*phase I only*). Selinexor dosing (at the same dose level) can be re-initiated once the patient's condition has stabilized clinically, even when the patient is taking antimicrobial or other agents.

Other DLTs: in the event of a DLT in Cycle 1 (*phase I only*), or other toxicity that warrants discontinuation in the opinion of the investigator, selinexor should be discontinued and the participant removed from study.

The following adverse events will not be considered DLTs (*phase I only*):

- Grade 3 nausea, vomiting or diarrhea (unless persisting > 3 days with appropriate treatment of anti-emetics or anti-diarrheals)
- Alopecia of any grade
- Weight loss of less than 20%
- Electrolyte or serum analyte (e.g., urate) abnormalities that are reversible with standard interventions

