Antineoplastic therapy: Concurrent cancer therapy, including chemotherapy (other than protocol drugs fludarabine, cytarabine and ITHMA), immunotherapy, or biologic therapy cannot be administered to patients while receiving selinexor.

Radiation therapy: Concurrent radiotherapy is prohibited.

Investigational agents: No other investigational agents may be given while the patient is on protocol therapy.

Growth factors: The routine use of filgrastim (G-CSF, Neupogen®) or other growth factors is discouraged, but may be used in cases of documented infection or sepsis during periods of neutropenia, according to institutional practice.

Conjunctivitis prophylaxis: Dexamethasone or prednisolone ophthalmic solution or artificial tears (e.g., hydroxymethylcellulose, hypromellose, polyvinyl alcohol), 2 drops in each eye every 4 hours while awake, should be used during cytarabine administration and for 24 hours after completion to prevent conjunctival irritation.

Drugs undergoing glutathione conjugation: The primary metabolism of selinexor is inactivation by glucuronidation; conjugation with glutathione is a secondary mode of metabolism. Because acetaminophen is associated with glutathione depletion, patients should not take acetaminophen on days of selinexor administration.

Prophylaxis and treatment of metabolic derangement: Care should be taken to prevent hyperuricemia and hyperphosphatemia in participants with large tumor burdens. Such participants should receive IV hydration at 1500-3000 mL/m²/day before the initiation of therapy, oral phosphate binders, and recombinant urate oxidase or allopurinol as needed.

Prophylaxis for *Pneumocystis jiroveci* pneumonia: All participants should receive prophylaxis for *Pneumocystis jiroveci* pneumonia according to institutional guidelines.

Prophylaxis for fungal infections: Because patients with relapsed leukemia are at high risk for fungal infections, all participants should receive antifungal prophylaxis according to institutional guidelines. Prophylaxis with voriconazole or posaconazole are strongly recommended.

Prophylaxis for bacterial infections: Because patients with relapsed leukemia are also at high risk for bacterial infections, all participants should receive antibiotic prophylaxis according to institutional guidelines. We recommend starting prophylactic antibiotics when the ANC \leq 1000 and falling or predicted to fall and continued until the ANC \geq 100 and rising.

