10.2 Recording and Reporting AEs and SAEs

Adverse events (AEs) will be evaluated and documented by the clinical staff and investigators throughout inpatient hospitalizations and each outpatient visit. CRAs are responsible for reviewing documentation related to AEs and entering directly into CRIS

protocol-specific database. The data to be recorded are 1) the event description, 2) the NCI CTCAE v4.0 code and grade, 3) the onset date, 4) the resolution date (or ongoing), 4) action taken for event, 5) patient outcome 6) relationship of AE to protocol treatment/interventions, 7) if AE was expected or unexpected, and 8) comments, if applicable.

AEs that are classified as serious, unexpected, and at least possibly related will be notated as such in the database as “SAEs”.

Attribution of an Adverse Event

Not related- The lack of a temporal relationship of the event to study treatment makes a causal relationship not reasonably possible, or other drugs, therapeutic interventions or underlying conditions provide a sufficient explanation.

Unlikely related- The temporal relationship of the event to study treatment makes a causal relationship reasonably unlikely, and other drugs, therapeutic interventions or underlying conditions may not provide sufficient explanation for the observed event.

Possibly related- The temporal relationship of the event to study treatment makes a causal relationship reasonably possible, and the event is more likely explained by exposure to the study treatment than by other drugs, therapeutic interventions or underlying conditions.

For the purpose of safety analyses, all AE’s that are classified as unlikely or possible will be considered treatment-related events.

These events will be reported expeditiously to the St. Jude IRB within the timeframes as described above. Cumulative summary of Grades 2-5 events will be reported as part of the progress reports to IRB at the time of continuing review. Specific data entry instructions for AEs and other protocol-related data will be documented in protocol-specific data entry guidelines, which will be developed and maintained by study team and clinical research informatics.

Patients with abnormal blood counts due to bone marrow involvement by disease (i.e. all leukemia patients and lymphoma patients with bone marrow involvement) will be considered non-evaluable for hematological toxicities.

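### Appendix IV's cytopenia rows contradict the body text on growth factors and on restart level, and do not say whether they govern the post-chemotherapy selinexor doses on Days 22 and 24

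*Combined protocol and SAP*

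**What the plan says.** **Schedule.** Section 4.1: "Selinexor will be given orally on days 1, 3, 8, 10, 22 and 24 of each cycle". Section 4.4 sets a "selinexor dose of 40 mg/m²/dose" for Phase II. The treatment outline at the front of the protocol states that fludarabine and cytarabine "will be given on days 16 through 20". Sections 4.1 and 4.4 attach no platelet or neutrophil condition to the Day 22 and 24 doses. If chemotherapy is brought forward, Section 4.1 has selinexor resume 3 days after it ends, again without a count condition.

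**Appendix IV, platelets.** Grade 3 without bleeding: once-weekly dosing at the same level. Grade 4 without bleeding: "Hold dosing until Grade ≤ 3 and follow above guidelines if Grade 3". Grade 3 or worse with petechiae or purpura: a 5-day hold and restart one level lower.

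**Appendix IV, neutrophils.** Grade 3 or 4 without fever: growth factors, no selinexor hold. Grade 3 or worse febrile neutropenia: growth factors, hold, restart one level lower.

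**Body text.** The heading of Section 4.6.2.3 refers the reader to Appendix IV. Its text says "Doses should be delayed, rather than omitted, for the following non-hematologic toxicities", and it allows selinexor to be re-initiated at the same level once a patient with Grade 4 infection or clinical sepsis has stabilized. Section 4.8 says routine growth-factor use "is discouraged, but may be used in cases of documented infection or sepsis during periods of neutropenia"; its missed-dose paragraph skips a dose missed by more than 24 hours. Section 10.2 states that leukemia patients whose abnormal counts come from marrow disease "will be considered non-evaluable for hematological toxicities".

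**The concern.** Appendix IV is operative text, so a site must apply it together with the treatment plan. The last two selinexor doses come just after drugs for which Sections 5.2 and 5.3 give myelosuppression as the main dose-limiting effect. Low counts at that point are foreseeable, and the appendix rows, read literally, reach those doses.

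Two careful sites could therefore treat the same patient differently: one gives Days 22 and 24 as scheduled, another holds them; one starts growth factors in afebrile neutropenia, another does not; one restarts at the same level after a septic febrile episode, another a level lower. At stake are consistent and safe dosing, and a clear description of the regimen behind a single-arm response rate collected at several sites.

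**Working it through.** **1. The plan's own figures.** Under the two-stage rule (continue at 8 or more of 28; success at 16 or more of 39), the probability of success is Σ over x = 8 to 28 of P(X₁ = x) · P(X₂ ≥ 16 − x), with X₁ ~ Bin(28, p) and X₂ ~ Bin(11, p). This gives 0.0943 at p = 0.30 and 0.9001 at p = 0.50, in line with the stated 10% and 90%. Nothing in this point alters those figures.

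**2. Planned exposure.** 6 doses × 40 mg/m² = 240 mg/m² per cycle.

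**3. Timing in Cycle 1.** Chemotherapy nominally ends on Day 20: 22 − 20 = 2 days and 24 − 20 = 4 days. With the ±2-day window in Section 4.1 it ends on Day 18 to 22, so Day 22 falls 0 to 4 days later and Day 24 falls 2 to 6 days later.

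**4. Possible loss from Days 22 and 24, by reading.**

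| Reading | Doses given | mg/m² given | Loss |
|---|---|---|---|
| Rows do not apply, or held doses fully made up | 6 | 240 | 0/240 = 0% |
| Both doses given one level lower | 6 | 4×40 + 2×30 = 220 | 20/240 = 8.3% |
| Once weekly in that week (Grade 3 row) | 5 | 5×40 = 200 | 40/240 = 16.7% |
| Both held and not made up (Grade 4 row) | 4 | 4×40 = 160 | 80/240 = 33.3% |

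The second row assumes that one level below 40 is the 30 mg/m² of Table 3. At the 15 mg/m² minimum in Appendix IV it would be 2 × 25 = 50, and 50/240 = 20.8%, still inside the 0% to 33% range.

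**5. Average loss.** If a fraction f of patients lost both doses and the rest lost none, the average loss would be f × 33.3%. The documents give no f. Assuming f from 0 to 1, the average runs from 0% to 33.3%.

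**6. The passages side by side.**

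| Question | Appendix IV | Body text | Relation |
|---|---|---|---|
| Growth factors, Grade 3/4 neutropenia without fever | Implement | 4.8: routine use discouraged; allowed in documented infection or sepsis | Contradiction |
| Restart level, febrile neutropenia that is also Grade 4 infection or sepsis | One level lower | 4.6.2.3: same level | Contradiction where the events overlap |
| Platelet hold on Days 22/24 | Hold or once weekly; cause of cytopenia not addressed | 4.1 and 4.4: no count condition; 10.2: disease-related cytopenia non-evaluable | Scope unresolved |
| Fate of a held dose | Hold; nothing on make-up | 4.6.2.3: delay rule for listed non-hematologic events only; 4.8: skip if missed by more than 24 hours | Not settled |

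**7. Endpoints.** Sections 8.1.1 and 8.1.2 separate CR from CRi partly at an ANC of 500/µL. Growth factors could move a patient across that line. Section 12.3 counts both CR and CRi as success, so the primary classification stays the same; the CR rate reported under Section 12.4 could shift.

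**The case against.** The best defence is that a toxicity hold does not contradict a planned schedule. Section 4.6.2.3 hands dose modification to Appendix IV, and its delay rule says how to handle the listed events; it does not forbid a hold for low platelets. A reader might infer that the body text bars hematologic holds. The documents do not support that: on thrombocytopenia the body is silent, so this part is a question of scope.

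A second tempting inference is that the regimen will lose a third of its selinexor. That figure needs both doses held and neither made up. Appendix IV says hold rather than omit, and its platelet rows also call for transfusions or platelet growth factors. Only the missed-dose paragraph of Section 4.8 could turn a hold into a lost dose, and it does not say whether it covers doses held for toxicity. Neutropenia without fever triggers no hold at all.

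Third, "During Cycle 1 patients should receive 5 of the 6 intended doses of selinexor" might be read as a Phase II requirement that 4 of 6 doses would breach. The sentence goes on to make a toxicity-related shortfall at Day 35 a DLT in Phase I only, and that phase is complete.

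Fourth, because Section 3.1 sets no platelet minimum, a reader might extend the rows to Day 1. Appendix IV is titled for events associated with selinexor, and cytopenia before the first dose is not such an event.

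Finally, the protocol deliberately allows variable exposure (early chemotherapy, single-agent continuation, transplant after Day 15), so the response rate can fairly be said to belong to a strategy that includes its modification rules.

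All of this stands. None of it removes the two contradictions or says whether the platelet rows cover disease- or chemotherapy-related cytopenia. The title does not settle that either: Section 2.1 lists thrombocytopenia among selinexor's common effects, so after chemotherapy a low platelet count could be attributed either way.

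**Conclusion.** The point holds as an unreconciled set of treatment rules. Growth-factor use in afebrile neutropenia is directly contradictory. Restart level is contradictory where febrile neutropenia and Grade 4 infection or sepsis coincide. Whether the thrombocytopenia rows govern the Day 22 and 24 doses, and whether held doses are made up, is left open.

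The possible loss for an affected patient is 0% to 33% of the cycle's selinexor (0 to 2 of 6 doses; 17% if that week becomes once weekly). This assumes 40 mg/m² for all planned doses and counts only Days 22 and 24. How often it would happen, the average loss, and any effect on response rate or power cannot be estimated from the documents. The growth-factor conflict costs no selinexor and, through the ANC criterion, can affect only the secondary CR rate.

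**What to change.** Reconcile Appendix IV with Sections 4.1, 4.4, 4.6.2.3, 4.8 (growth factors and missed doses) and 10.2. The amended text should:

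- state whether the hematologic rows apply to disease- or chemotherapy-related cytopenia during the combination cycle, and so to Days 22 and 24;
- state whether doses held for cytopenia are made up or skipped;
- make the two growth-factor statements agree;
- make the restart-level statements agree for febrile neutropenia that is also Grade 4 infection or sepsis.

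The sponsor decides which rule stands; this review proposes none. The cost is a clarifying amendment, with no extra patients or procedures and no change to the Phase II design.
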